# **invisa-RED IR REHAB Clinical Trial Protocol**

## **Purpose of the Study**

The trial is designed to provide data with which to evaluate the efficacy and safety of the invisa-RED® IR REHAB Low-level Laser Therapy (LLLT) device as compared with a sham device when used for the adjunctive treatment of nociceptive musculoskeletal pain . This will be a single blind trial of two groups of equal number; one group will be treated as usual, the other treated using a sham device. At the conclusion of the trial; results from the two groups will be statistically analyzed to determine the efficacy of the IR REHAB machine for the adjunctive treatment of musculoskeletal pain.

## **Background**

“Musculoskeletal pain is a challenging condition for both patients and physicians. Many adults have experienced one or more episodes of musculoskeletal pain at some time of their lives, regardless of age, gender, or economic status. It affects approximately 47% of the general population. Of those, about 39–45% have long- lasting problems that require medical consultation. Inadequately managed musculoskeletal pain can adversely affect quality of life and impose significant socioeconomic problems.” The invisaRED® IR REHAB has been developed to deliver adjunctive pain therapy for musculoskeletal pain.

## **Criteria for Participants**

The number of participants is projected to be thirty (30).

There will be an equitable distribution of male and female participants.

Women who are pregnant, trying to get pregnant, or nursing will be excluded from the study, as they should not receive Low-level Laser Therapy (LLLT). There is no evidence of harm to a an unborn baby however there have been no safety tests either, so for medical legal reasons we recommend never treating such individuals.

The participants will be 18 years or older.

The ethnicity of the participants will be equitably distributed.

Inclusion criteria will be individuals that may benefit from an adjunctive therapy for nociceptive musculoskeletal pain.

---

 El-Tallawy, Salah N et al. “Management of Musculoskeletal Pain: An Update with Emphasis on Chronic Musculoskeletal Pain.” *Pain and therapy* vol. 10,1 (2021): 181-209. doi:10.1007/s40122-021-00235-2

## **Subject Qualification**

No candidates of diminished capacity will be considered for inclusion in the trial.

Capacity is a functional assessment and a clinical determination about a specific decision that can be made by any clinician familiar with a patient's case. The four key components addressed during the candidates capacity evaluation include: 1) communicating a choice, 2) understanding, 3) appreciation, and 4) rationalization/ reasoning.

No monetary remuneration will be offered participants in the study. At the conclusion of the clinical trial, and upon approval by the FDA, a commensurate number of treatments with the IR REHAB device will be offered to those patients who received treatment using the sham device. This will provide the participants treated with the sham device the opportunity to undergo therapy using an activated IR REHAB device.

All persons interviewed for the trial will be selected using the established invisaRED Technologies IR REHAB guidelines for indications and contraindications. Combining the guidelines for indications and contraindications with the thorough classroom review and "hands on training " for clinicians who will be conducting the trial, the risk is best compared to exposure to sunlight.

Subjects of the study receiving the invisaRED Technologies IR REHAB therapy may receive the following benefits:

- Open up blood vessels to increase circulation and ease swelling
- Help your immune system create more chemicals that heal tissue
- Build more connective tissue in injured area
- Trigger endorphins, natural hormones that ease pain
- Drug free alternative without a chance of addiction
- Noninvasive therapy
- No known side effects

## **Criteria for Participants:**

Participants will be taken from a random population of respondents to email and social media recruitment, in person offers to participate to existing patients, and individuals in the community who have seen signage advertising the trial. The number of participants is projected to be thirty (30). There will be an equitable distribution of male and female participants. The participants will be older than the age of 18 years. Inclusion criteria will be individuals that may benefit from an adjunctive therapy for nociceptive musculoskeletal pain.

**Exclusion criteria will include the following:**

- For women who are pregnant, trying to get pregnant or nursing, laser light therapy should be received only after the end of these conditions. There is no evidence of harm to an unborn baby however there have been no safety tests either, so for medical legal reasons we recommend against treatment during these times.
- Individuals with uncontrolled hypertension, light sensitive epilepsy, cancer, heart disease, infectious skin disease, and severe varicose veins should not use this device.
- People suffering from infectious and acute disease such as a fever should not use this device.
- People who have hemorrhagic disease, vascular ruptures, skin inflammation, or any disease of the skin should not use this device.
- Person with a history of lentigines, an autoimmune vascular disease that causes color changes in the legs or arms due to obstruction or stenosis of blood vessels.
- A person with a history of erythema, an acquired, long-lasting reticulocyte red and pigmented rash, caused by persistent or repeated exposure to intense heat or infrared radiation.
- Persons who are susceptible to or have a history of herpes in the treatment area
- Anyone who has experienced problems subsequent to previous laser treatments
- People who have immune system dysfunction such as Leukemia, Hemophilia, etc., and light sensitive persons should not use this device.
- Use of laser light therapy in the ears, nose, eye, or throat is not recommended.
- Individuals with a history of melanoma, raised moles, suspicious lesions, keloid scar formation, or healing problems should not undergo laser light therapy
- Individuals with active infections, open lesions, hives, herpetic lesions, cold sores, or tattoos and permanent make-up in the area of treatment should not undergo laser light therapy.
- People who have used isotretinoin (commonly known as Accutane), tetracycline, St. John's Wort, or any photo sensitizing drugs in the last year should not undergo laser light therapy.
- Individuals with autoimmune diseases such as Lupus, Scleroderma, or Vitiligo should not undergo laser light therapy.

## **Exclusion Criteria - continued**

- Individuals who have pacemakers or other electro-stimulation devices surgically implanted should not undergo laser light therapy.
- Any insulin dependent individual should consult their physician before undergoing laser light therapy.
- All individuals considered “vulnerable” such as children, pregnant women, nursing home residents or other institutionalized persons, students, employees, fetuses, prisoners, and persons with decisional incapacity.

## **Subject Identification, Recruitment And Consent/Assent**

At roadway intersections in close proximity to the AbbyCare/IR Medical Centers Clinic located at [name] road side signs will be erected containing the verbiage: “Pain and Injury Study, No Cost, Call [contact]”

This will be done in order to recruit study volunteers from the community. The clinic’s primary care patients will also be provided an opportunity to volunteer for consideration as a trial participant. The primary investigator will conduct all subject interviews and obtain informed consent. A thorough disclosure of all clinical process, contraindications, and any risk will be discussed with candidates for the trial. All candidates will be older than the age of majority in the state of Georgia (18 years old). There shall be no cost incurred by candidates for inclusion in the study or individuals selected to participate in the study.

## **Methods and Procedures**

The trial is designed to prove the efficacy and safety of the invisa-RED Technology IR REHAB device when used as prescribed as an adjunctive therapy for musculoskeletal pain. The trial will compare results between two groups; the first will be treated using the invisa-RED Technology IR REHAB and the second group with a sham (placebo) device.

The trial will be conducted employing a single blind study methodology; participants will not know to which trial group they have been randomly assigned. Participants randomly selected for the control or Sham (placebo) Group will undergo therapy sessions with a disabled IR REHAB device producing no laser energy, however, this sham device will power up the console and fans to appear to be operating normally. If a participant questions the efficacy of the sham device, an assertion may be made that only a near infrared, non-visible frequency of light, is being employed. The control group receiving treatments using the sham device will be scheduled for treatment at times other than participants who will undergo therapy sessions with the fully functioning device in order to ensure the trial blind.

All participants will undergo treatments 2 times weekly for 3 weeks. Treatment will be 15 minutes each session. For each 15 minute session a singular adjustment to the laser’s power output will be made based on the participants standard Fitzpatrick Skin Type. This power adjustment ensures optimal photonic energy absorption, enhanced efficacy, and participant safety. The minimum time between any participants’ scheduled treatments will be 48 hours.

## **Methods and Procedures - continued**

Prior to each therapy session the participant will be asked to record their pain level using a Visual Analog Scale (VAS) and then in the same manner after each treatment using the same Visual Analog Scale (VAS). The results from the two groups will be statistically analyzed to determine the efficacy of the invisa-RED Technology IR REHAB as an adjunctive therapy for nociceptive musculoskeletal pain. Any medical errors will be included in the statistical analysis.

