## **Data Storage and Security**

All individuals participating in the trial will be assigned a participant number. Subsequently all clinical records and reports will reference only the participant number, ensuring that participants remain anonymous. Because of the low number of trial participants, only paper records will be maintained for all clinical and personal data. Records will be kept in locked storage and physical access will only be on a need to know basis. A participants' personal data correlating the participating individuals name and the trial participants Identifying Number will only be available to the principal investigator, clinical staff, and the trial administrator. All analytics will be performed on securely encrypted devices using only data masked or redacted of any personal information.

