## **Analysis**

To examine the research question, independent sample *t*-tests using the statistical analysis program IBM SPSS ver.30 will be conducted on the data set. The data set will be comprised of comparative results from the two trial groups, the Care as Usual Study Group and the Sham (placebo effect) Study Group. The tests will be bootstrapped to a test size of N=20,000 for validation.

An independent samples *t*-test is the appropriate statistical test when the purpose of research is to assess if differences exist on a continuous (interval/ratio) dependent variable by a dichotomous (2 groups) independent variable. The continuous dependent variable to be tested is the change in pain level of the joint or body area treated during the clinical trial. Each participant will be asked to indicate on a standard 100mm Visual Analog Scale their pain levels before the first treatment and after each of the prescribed treatments. The difference between the initial pain level of a participant and the level of pain indicated after their sixth and final treatment will be statistically analyzed to determine if there is a significant difference between those in the Care As Usual Group and the Sham (placebo) Group.

The dichotomous independent variables for the data set is the change in pain level of each participant in the group treated with the invisa-RED Technology IR REHAB Low-level Laser Therapy (LLLT) device and the group treated using the sham (placebo) device as a therapy in the standardized clinical protocol. The assumptions of normality and homogeneity of variance will be assessed. Homogeneity of variance assumes that both groups have equal error variances and will be assessed using Levene's Test for the Equality of Error Variances. Each *t*-test will be two tailed with the probability of rejecting the null hypothesis when it is true set at  $p < 0.05$ . This ensures a 95% certainty that the differences did not occur by chance. Data produced by both groups will be the results of a clinical trial governed and conducted as a randomized single - blind study using an IRB approved clinical protocol.

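### Only participants are blinded, and nothing provides for private completion or arm-masked measurement of the VAS, so staff influence on the only efficacy outcome cannot be excluded

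*Combined protocol and SAP*

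**What the plan says.** **Blinding.** The protocol's Methods and Procedures section describes a "single blind study methodology; participants will not know to which trial group they have been randomly assigned". No other role is said to be unaware of the arm. Sham participants are "scheduled for treatment at times other than participants who will undergo therapy sessions with the fully functioning device", and a reply is prepared for a participant who doubts the sham device.

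**Rating.** Methods and Procedures - continued states: "Prior to each therapy session the participant will be asked to record their pain level using a Visual Analog Scale (VAS"). A second rating on that scale follows once the session ends. The SAP's Analysis section has each participant "indicate on a standard 100mm Visual Analog Scale their pain levels before the first treatment and after each of the prescribed treatments". Its primary comparison uses the first of these ratings and "the level of pain indicated after their sixth and final treatment". Neither section names the person who asks for the mark or the person who measures it. Neither fixes the wording of the request, or says whether the participant is alone or can see earlier marks.

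**Masking of data.** Data Storage and Security says that analysis will be done "using only data masked or redacted of any personal information". That covers identity, not trial arm. The same section keeps records on paper. It gives the principal investigator, clinical staff and trial administrator the key that links names to participant numbers.

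**Outcome.** Change in VAS pain is the only efficacy outcome under Outcome Measures.

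**The concern.** Pain on a VAS is subjective, and here it is recorded in the clinic directly before and after contact with the treating staff. Someone who knows the arm could affect it in two ways. Tone, prompting or visible interest could shift where the participant places the mark. Knowledge of the arm could also colour how the mark is read in millimetres.

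If either acts differently in the two arms, it adds directly to the difference in mean change, and the t-test cannot separate it from a device effect. There is no second efficacy outcome against which to check the result. The final rating follows the sixth session, so it is taken straight after contact with staff.

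**Working it through.** **Step 1: do staff know the arm?** No sentence says so. To hold sham sessions at separate times and to use the prepared reply, at least some clinic staff must know which device is in use. Staff knowledge is therefore a strong inference. That the device operator also collects the VAS is not stated and does not follow.

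**Step 2: is the rating or its measurement protected?** The relevant sections give:

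| Safeguard | Where one would look | Found |
|---|---|---|
| Participant unaware of arm | Methods and Procedures | Yes |
| Participant makes the mark | Methods and Procedures - continued; Analysis | Yes |
| Collector unaware of arm | same sections | Not stated |
| Private completion, fixed wording, earlier marks hidden | same sections | Not stated |
| Measurement with arm withheld | Analysis; Data Storage and Security | Not stated; only personal information is masked |

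**Step 3: reproduce the reported figures.** Inputs are the arm means of 61.46 and 19.79 (Outcome Measures), Cohen's d of 1.44 (Study Results), and 16 and 13 participants analysed.

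- Difference: 61.46 − 19.79 = 41.67, as reported.
- Implied SD: 41.67 / 1.44 = 28.94.
- Standard error: 28.94 × √(1/16 + 1/13) = 28.94 × 0.3734 = 10.81.
- t = 41.67 / 10.81 = 3.86 on 27 degrees of freedom, p = 0.0006. The report gives p < 0.01.
- 95% interval: 41.67 ± 2.052 × 10.81 = 19.5 to 63.8. The bootstrap interval reported is 20.15 to 61.67.
- Power by noncentral t, two-sided 0.05: 96.0%. The post-trial figure reported is 95.7%.

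The SD of 28.94 is therefore a sound basis for the next step.

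**Step 4: subtract an assumed staff influence b.** The documents give no value for b, so the range is an assumption. The adjusted difference is 41.67 − b, and its t is (41.67 − b) / 10.81. The last column is the chance, with no true effect, of a significant result favouring the device: P(T > 2.052), where T is noncentral t with 27 degrees of freedom and noncentrality b / 10.81.

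| b (points) | Share of 41.67 | Adjusted difference | p | False positive favouring the device |
|---|---|---|---|---|
| 0 | 0% | 41.67 | 0.0006 | 2.5% |
| 5 | 12% | 36.67 | 0.002 | 6.5% |
| 10 | 24% | 31.67 | 0.007 | 14.3% |
| 20 | 48% | 21.67 | 0.055 | 43.1% |

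**Step 5: tipping points.** The lower limit reaches zero at b = 19.5 with the t interval, or b = 20.15 with the bootstrap interval. The estimate falls to the 30 points used for planning at b = 41.67 − 30 = 11.67.

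**The case against.** The strongest reply is that the design already limits observer influence. Participants are blinded and make the mark themselves. The sham console switches on and its fans run, and session times are kept apart to protect the blind. Reading a 100 mm line leaves little room for judgement, so a systematic misreading of 5 to 10 mm is less plausible than cueing. On the figures above, 5 or 10 points would leave the result significant, and nothing shows that any such influence occurred. All of this stands, and it limits the size of the point. It does not close the gap: a blinded participant can still be cued by someone who knows the arm, and nothing in the documents guards against that.

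Three stronger readings are tempting, and the documents do not support them.

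- A reader might infer that unblinded operators asked for every rating. Both sections that describe the rating are silent on who asks.
- A reader might infer that private completion would remove the influence. It acts only at rating. Contact during six 15-minute sessions, the comfort check at the start of each session (Risk/Benefit Assessment - cont.) and the prepared reply would remain.
- A reader might infer that sheets bearing only the participant number would mask the arm without extra staff. Staffing is not described. Clinical staff hold the name-number key, and session times differ by arm, so with about 30 participants a number may reveal the arm.

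**Conclusion.** The point holds as a gap in protection against bias, not as evidence that bias occurred. One group is blinded, staff very probably know the arm, the only efficacy outcome is a subjective mark made in the clinic, and neither the rating nor its measurement is shielded from knowledge of the arm.

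The size is unknown. The illustration rests on an assumed 5 to 10 points acting wholly in the device's favour, an SD of 28.94 derived from the reported d, and a constant shift that leaves the SD unchanged. Within that range the estimate is weakened but the significance of the result is not overturned. The documents give 41.67 both as a VAS score difference (Outcome Measures) and as a percentage (Study Results). The calculation takes it as points, and the thresholds carry that ambiguity.

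This is a cheap improvement that should be made. It is not a reason to set the result aside.

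**What to change.** **Protocol text (Methods and Procedures - continued).** State that:

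1. for each rating the participant receives a fresh, unmarked VAS sheet with a fixed, neutral instruction;
2. the participant marks the sheet alone and seals it;
3. all sheets are measured in one batch, before the arm code is linked to the data;
4. the sheets are measured under a separate measuring code that staff who ran sessions or hold the name-number key cannot trace to an arm.

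**For this trial.** Recruitment ended in August 2024 and results are reported, so private completion can no longer affect these data. The sponsor can still:

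- re-measure the retained paper sheets with the arm withheld;
- state who collected and who measured the marks, and whether they knew the arm;
- report the limitation beside the statement in Conclusions That May Be Drawn From The Study.

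**Cost.** Envelopes, a paragraph of protocol text, a coding step and one measuring session. Whether existing staff can do this cannot be judged from the documents. An incomplete mark would be found later than it would be with an open sheet. Sample size, significance level and power do not change.

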## **Data Analysis and Data Monitoring**

The mean change in each group of participant's pain levels as recorded at the trials beginning and then at the trials conclusion will be statistically evaluated using a two-tailed independent sample T-test with an a priori threshold p value of < (less than) 0.05.

## **Monitoring Plan**

The study is classified as a minimal risk trial of short duration therefore a detailed plan for monitoring the data for participant safety is not required.

## **Data Storage and Security**

All individuals participating in the trial will be assigned a participant number. Subsequently all clinical records and reports will reference only the participant number, ensuring that participants remain anonymous. Because of the low number of trial participants, only paper records will be maintained for all clinical and personal data. Records will be kept in locked storage and physical access will only be on a need to know basis. A participants' personal data correlating the participating individuals name and the trial participants Identifying Number will only be available to the principal investigator, clinical staff, and the trial administrator. All analytics will be performed on securely encrypted devices using only data masked or redacted of any personal information.

## **Risk/Benefit Assessment**

Applying the test for the determination of risk established by the FDA Regulation referred to as the "Common Rule" found in 45 CFR 46, Subpart A the rule states;

*"Minimal risk means that the probability and magnitude of harm or discomfort anticipated in the research are not greater in and of themselves than those ordinarily encountered in daily life or during the performance of routine physical or psychological examinations or tests.*

We have determined that only a minimal risk is presented to participants of the trial

See the detail minimal risk criteria analysis below:

- I) The device is NOT intended as an implant that presents a potential for serious risk to the health, safety, or welfare of a subject. The invisa-RED IR REHAB employs no implanted devices as part of any treatment or therapy.
- II) The device is NOT purported or represented to be for a use in supporting or sustaining human life that presents a potential for serious risk to the health, safety, or welfare of a subject.
- III) The invisa-RED IR REHAB is only to be used as directed as an adjunctive therapy for nociceptive musculoskeletal pain and is not represented or employed as a life sustaining device or therapy.

